**Confidential**

Protocol #: COVMOPO0561

Rev E 09AUG2017

**1. Revision History**

[REDACTED]	[REDACTED]	[REDACTED]	[REDACTED]
[REDACTED]	[REDACTED]	[REDACTED]	[REDACTED]
[REDACTED]	[REDACTED]	[REDACTED]	[REDACTED]
[REDACTED]	[REDACTED]	[REDACTED]	[REDACTED]

This document is electronically controlled. Printed copies are considered uncontrolled.

		[REDACTED]	
[REDACTED]	[REDACTED]	[REDACTED]	
[REDACTED]	[REDACTED]	[REDACTED]	

This document is electronically controlled. Printed copies are considered uncontrolled.

**Confidential**

Protocol #: COVMOPO0561

Rev E 09AUG2017

**Confidential**

Protocol #: COVMOPO0561

Rev E 09AUG2017

### 3. Glossary

Term	Abbreviation	Definition
Adverse Event	AE	
Any untoward medical occurrence, unintended disease or injury, or untoward clinical signs (including abnormal laboratory findings) in subjects, users or other persons, whether or not related to the medical device.
 
NOTE 1: This definition includes events related to the medical device or the comparator.
 
NOTE 2: This definition includes events related to the procedures involved.
 
NOTE 3: For users or other persons, this definition is restricted to events related to the medical devices.

American Heart Association	AHA	
A non-profit organization in the United States that fosters appropriate cardiac care in an effort to reduce disability and deaths caused by cardiovascular disease and stroke.
 
The AHA published guidelines in 2003 for telemetry monitoring that are still applicable and being used currently.

Adverse Device Effect	ADE	Adverse event related to the use of a medical device.
Clinical Investigation Plan	CIP	The present document describing the study protocol.
CIP Deviation	CIP Deviation	An event when the investigator or site personnel did not conduct the study according to the CIP or the clinical trial agreement. Medtronic's term for protocol deviation.
Case Report Forms / Electronic CRF	CRF/eCRF	Forms where the clinical data are collected. eCRF is the electronic version of the CRF.
Device Deficiency	DD	
Inadequacy of a medical device with respect to its identity, quality, durability, reliability, safety or performance.
 
NOTE 1: This definition includes adverse events resulting from insufficient or inadequate instructions for use, deployment, implantation, installation, or operation, or any malfunction of the medical device.
 
NOTE 2: This definition includes any event resulting from use error or from intentional misuse of the medical device

Electrocardiogram	ECG	A clinical technique measuring transthoracic electrical activity of

This document is electronically controlled. Printed copies are considered uncontrolled.

Term	Abbreviation	Definition
		the heart over time.
Electronic Data Capture	EDC	Electronic system where the data are collected through the eCRF (Oracle Clinical). May also be referred to as RDC (Remote Data Capture).
Emergency Department	ED	Medical treatment facility specializing in emergency medicine, the acute care of patients who present without prior appointment; either by their own means or by that of an ambulance.
Electronic Medical Record	eMR	Digital version of a patient's medical record within a single facility.
Food and Drug Administration	FDA	Federal agency of the United States Department of Health and Human Services; regulates medical devices.
Heart Rate	HR	A unit of measure that indicates speed of heartbeat in beats per minute.
Intensive Care Unit	ICU	A hospital unit with concentrated special equipment and specially trained personnel for the care of seriously ill patients requiring immediate and continuous attention
Informatics Manager	IM	A type of software that is intended to route and store medical device data and device diagnostic information from supported devices to the VPMP, 3rd Party Annunciation Systems, Electronic Medical Record (eMR) and Clinical Information System (CIS).
Institutional Review Board	IRB	An independent body in US, consisting of healthcare professionals and non-medical members, whose responsibility is to protect rights, safety and well-being of human subjects involved in a clinical trial and to provide public assurance of that protection, by, among other things, expressing an opinion on the clinical trial protocol, the suitability of the investigators involved in the trial and the adequacy of facilities, and on the methods and documents to be used to inform trial subjects and obtain their informed consent.
Investigator Site File	ISF	Regulatory binder supplied by the sponsor.
Length of stay	LOS	The overall hospital length of stay, time of admission to discharge.
Post-anesthesia care unit	PACU	Hospital until typically attached to an operating suite that provide care to patients recovering from anesthesia
Product Accountability Log	PAL	A log maintained by investigative site personnel to document that the study product (s) have been used according to the protocol, and to document the final accounting of study product(s) received at the site, dispensed to subjects, returned by the subjects, and returned to the sponsor.

This document is electronically controlled. Printed copies are considered uncontrolled.

Term	Abbreviation	Definition
Patient-controlled analgesia	PCA	A drug-delivery system that dispenses a preset intravascular dose of a narcotic analgesic when the patient pushes a switch on an electric cord.
Rapid Response Team	RRT	A team of health care providers that responds to hospitalized patients with early signs of clinical deterioration on non-intensive care units to prevent respiratory or cardiac arrest.
Respiration Rate	RR	A unit of measure that indicates rate of breathing in breaths per minute.
Serious Adverse Event	SAE	
Adverse event that
 
 
1. led to death,
 
2. led to serious deterioration in the health of the subject, that either resulted in 
 
a. a life-threatening illness or injury, or
 
b. a permanent impairment of a body structure or a body function, or
 
c. in-patient or prolonged hospitalization, or
 
d. medical or surgical intervention to prevent life-threatening illness or injury or permanent impairment to a body structure or a body function,
 
 
 
3. led to fetal distress, fetal death or a congenital abnormality or birth defect
 
 
Note: Planned hospitalization for a pre-existing condition, or a procedure required by the protocol, without serious deterioration in health, is not considered a serious adverse event.

Serious Adverse Device Effect	SADE	Adverse device effect that has resulted in any of the consequences characteristic of a serious adverse event.
Surveillance Monitoring	SM	The SM group will serve as the group who will be monitored by the study device for the duration of study enrollment on a medical-surgical unit(s).
Standard Operating Procedures	SOP	Medtronic Quality Standard Operating Procedures
Telemetry Monitoring	TM	The TM group will serve as the control group in this study and will be monitored via the site's standard of care telemetry practice/protocol.
Vital Sync™ Informatics Manager & Virtual Patient Monitoring Platform	Vital Sync™ IM & VPMP	A software only device that provides mobile and centralized remote monitoring.
Virtual Patient Monitoring Platform	VPMP	A display system that provides visual and audible renderings of physiologic data, waveforms, alarms and alerts routed through the Vital Sync™ IM from supported devices. The Vital Sync™

This document is electronically controlled. Printed copies are considered uncontrolled.

Term	Abbreviation	Definition
		VPMP displays information received from the IM on any web-enabled device.

This document is electronically controlled. Printed copies are considered uncontrolled.

**Confidential**

Protocol #: COVMOPO0561

Rev E 09AUG2017

## 4. Synopsis

Title	A Prospective Evaluation of Surveillance Monitoring as an Alternative to Telemetry in Patients Scheduled for Telemetry without AHA Indication
Clinical Study Type	Post-market
Product Name	Vital Sync™ Informatics Manager & Virtual Patient Monitoring Platform (Vital Sync™ IM & VPMP) BioModule™ BH3-M2 sensor
Sponsor	Medtronic
Investigation Purpose	The purpose of the study is to evaluate the impact of surveillance monitoring versus telemetry monitoring on clinical, healthcare economics, resource utilization, and qualitative outcomes.
Product Status	Vital Sync™ IM & VPMP [REDACTED] and the BioModule™ BH3-M2 sensor are Class II devices and 510(k) cleared by the FDA.
Primary Objective	The primary objective of this study is to compare hospital length of stay (LOS) between the surveillance monitoring (SM) and telemetry monitoring (TM) period on patients without AHA telemetry indication.
Secondary Objectives	
Healthcare Economic and Resource Utilization Objectives
 
 
1. Compare telemetry bed, emergency department (ED) bed, and intensive care unit (ICU) bed availability between monitoring periods
 
2. Compare associated health care costs between monitoring periods
 
3. Compare the number of ICU, ED, post-anesthesia care unit (PACU), and telemetry delays in transfer between monitoring periods
 
4. Compare the number of hospital unit transfers between monitoring groups
 
5. Compare the number of unplanned ICU transfers between monitoring groups
 
6. Compare ICU LOS for subjects having unplanned transfers to the ICU between monitoring groups
 
7. Compare the number of unnecessary diagnostic tests and therapeutic procedures generated by artifacts and/or misdiagnosis between monitoring groups
 
 
Clinical and Qualitative Objectives
 
 
1. Compare the number of Rapid Response Team (RRT) interventions between monitoring groups
 
2. Compare survival rates post RRT interventions between monitoring groups
 

This document is electronically controlled. Printed copies are considered uncontrolled.

**Confidential**

Protocol #: COVMOPO0561

[REDACTED] Rev E 09AUG2017 [REDACTED]

	
 
3. Compare code blue rates between monitoring groups
 
4. Compare unplanned intubations between monitoring groups
 
5. Compare time of RRT activation to time of threshold notifications from SM system following clinical deterioration events
 
6. Assess clinical team satisfaction with surveillance monitoring and study product
 
7. Assess patient satisfaction with surveillance monitoring and study product
 
8. Assess perceptions of clinicians who prescribe telemetry to patients without AHA indication
 
9. Assess clinicians' perceptions on telemetry utilization and impact on hospital resource utilization and patient flow
 

Study Design	
This will be single-center, prospective, pilot, pre/post implementation study to collect post-market data on hospitalized subjects monitored via telemetry monitoring and surveillance monitoring.
 
The planned duration of the study is greater than or equal to six months. The TM (control) group will complete enrollment first over an estimated three month period, followed by an estimated three month enrollment period for the SM group.
 
Subject participation will last less than or equal to the duration of the hospital stay. Each subject will be followed in the hospital for a maximum period of 30 days (<math>\pm</math> 2 days) from the start of enrollment. No follow-up will occur after subjects are discharged from the hospital.

Sample Size	The subject population will include up to a total of 440 subjects with up to 220 subjects in each monitoring group.
Inclusion/Exclusion Criteria	
Inclusion Criteria: Each subject must meet the following criteria to be enrolled in the study:
 
 
1. Signed and dated informed consent by subject
 
2. Male or female 18 years of age or older
 
3. Expected hospitalized admission on the general care floor or medical surgical unit for at least one overnight stay and/or >12 hours
 
4. Scheduled for telemetry monitoring
 
5. Diagnosis indicates AHA telemetry Class III or none and therefore not indicated for telemetry monitoring
 
6. For SM group subjects, treating provider who scheduled subject for telemetry agrees to alternative monitoring plan of surveillance monitoring
 
7. Willingness to have study devices attached and hair shaved at sensor location as needed during study participation
 
8. Willingness to participate in all aspects of the study
 
 
Exclusion Criteria: Subjects who meet any of the following criteria will be excluded from the study:
 
 
1. Implanted pacemaker or automatic defibrillator
 
2. Allergy or sensitivity to ECG leads or adhesives that are similar to ECG leads
 
3. Current AHA Class I or II indication/prescription for telemetry monitoring
 
4. Prescription for other continuous condition monitoring such as capnography or pulse oximetry
 

This document is electronically controlled. Printed copies are considered uncontrolled.

	
 
5. Ongoing opioid therapy by PCA, by epidural or intrathecal infusions or by intravenous analgesia, per Investigator discretion
 
6. Ventilated or intubated patients at the time of enrollment
 
7. Female subject is pregnant, lactating, trying to get pregnant, or has a positive pregnancy test for women with childbearing potential
 
8. Condition that, in the opinion of the investigator, may prevent completion of the study or protocol requirements
 
9. Subject is considered as being morbidly obese (defined as BMI >50.0)
 

Study Procedures and Assessments	
Subjects who meet all of the inclusion criteria and none of the exclusion criteria will be assigned to either one of the monitoring groups and then followed for the duration of their hospital stay.
 
The monitoring groups will be enrolled in two prospective phases: telemetry monitoring (TM) OR surveillance monitoring. Enrollment of the TM group will occur first. After TM enrollment is complete, the enrollment phase of SM will initiate.
 
The TM group will serve as the control group and will be monitored via the site's standard of care telemetry practice/protocol. Subjects will continue to be enrolled in the study if subjects are transferred to medical-surgical unit after initial period of TM. No additional monitoring will be used for duration of study enrollment.
 
The SM group will undergo placement of the study device following study enrollment and hospital staff will implement the SM strategy for the duration of study enrollment. A dedicated medical-surgical unit(s) will be utilized for the SM phase.
 
Study procedures during the hospital stay will involve assessing eligibility, collecting baseline information, documenting clinical data from the eMR, unit transfers, discharges, and evaluating changes in health status.
 
All study related subject data will be documented and entered into the subjects' eCRF. All treatment will be standard of care per institutional practice.

Safety Assessments	Subjects will be monitored for Serious Adverse Events and Device-Related Adverse Events as noted in Section 12.
Statistics	Baseline and study outcomes will be summarized using descriptive statistics. One-way analysis of variance will be used to compare continuous variables (e.g., age, length of study) and Chi-square or Fisher's exact test will be used for categorical variables. Multivariate regression will be used to assess impacts of potential confounders. A P-value <0.05 is considered statistically significant unless otherwise specified.

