**13. Statistical Design and Methods**

**13.1. Sample Size Justification**

The study sample size is based on the primary non-inferiority objective of comparing hospital length of stay (LOS) between the surveillance monitoring (SM) and telemetry monitoring (TM) period on subjects without AHA telemetry indication. From similar study data published in the literature, we assume a similar LOS distribution for both monitoring groups with a common coefficients of variation of 0.65. With a pre-specified non-inferiority margin of 0.2 for the mean ratio, a sample size of 132 in each group will provide more than 80% power to assess the objective at the significance level of 0.05. Assuming at least 30% attrition from withdrawals and screen failures, up to 220 recruited subjects in each monitoring group will be used for this study.

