**13.2. Hypotheses and Endpoints**

The primary study endpoint is hospital of length of study (LOS), which is calculated from date of admission and discharge. The primary objective is to demonstrate that LOS of the SM group is similar (non-inferior) to the TM group.

[Redacted]

This document is electronically controlled. Printed copies are considered uncontrolled.

Additionally, if the non-inferiority objective is met, superiority will also be assessed (without statistical penalty) to further understand the effectiveness of SM versus TM. The corresponding superiority hypothesis [REDACTED] e., SM has shorter LOS duration than TM).

Secondary clinical and qualitative endpoints include:

- number of RRT interventions between monitoring groups
- survival rates post RRT interventions between monitoring groups
- Time of RRT activation to time of threshold notifications from SM system following clinical deterioration events
- code blue rates between monitoring groups
- unplanned intubations between monitoring groups
- clinical team satisfaction with surveillance monitoring and study product
- patient satisfaction with surveillance monitoring and study product
- perceptions of clinicians who prescribe telemetry to patients without AHA indication
- Clinicians' perceptions on telemetry utilization and impact on hospital resource utilization and patient flow

Additionally, healthcare economic and resource utilization data will be collected to evaluate:

- telemetry bed, ED, and ICU bed availability between monitoring periods
- associated health care costs between monitoring periods
- the number of ICU, ED, PACU, and telemetry delays in transfer between monitoring periods
- the number of hospital unit transfers between monitoring groups
- the number of unplanned ICU transfers between monitoring groups
- ICU LOS for subjects who have an unplanned transfer to the ICU between monitoring groups
- the number of unnecessary diagnostic tests and therapeutic procedures generated by artifacts and/or misdiagnosis between monitoring groups

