### 13.3. Statistical Analysis

In general, descriptive statistics will be used to summarize baseline and study outcomes. For continuous variables, number of available observations, mean, standard deviation, median, minimum and maximum values will be provided. For categorical variables, frequency and percentage will be used. Unless otherwise specified, statistical assessments will be based on 2-sided tests at an alpha level of 0.05, which include Student-t or Wilcoxon rank-sum or ANOVA test for continuous variables, and Chi-square or Fisher's exact test for categorical variables. Multivariate regression models will be used to assess impacts of potential confounding variable. [REDACTED].

The primary effectiveness analysis will be based on all evaluable data from this study. A per protocol analysis will be performed based on all subjects who are compliant with the study protocol, i.e. who provide valid informed consents.

For safety assessments, adverse events (AEs) will be summarized using frequency counts and percentages. Descriptive statistics will be provided by monitoring group and by severity and relationship. Additionally, differences between the two monitoring groups will be summarized along with 95% confidence intervals. Individual listings of adverse events, including event type, start date, duration,

This document is electronically controlled. Printed copies are considered uncontrolled.

Monitoring visits will be conducted at the start, during and at the closure of the clinical study in accordance with Medtronic internal SOPs and the Monitoring Plan. An interim monitoring visit may be combined with the closing monitoring visit.

Frequency of monitoring visits will occur based on subject enrollment, duration of the study, study compliance, findings from previous monitoring visits and any suspected inconsistency in data that requires investigation. Regulatory documents (e.g., Informed Consent Form, IRB approval letters and Clinical Trial Agreements, etc.) will be reviewed at the study center.

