**Confidential**

## 7.2. General Methodology

In general, descriptive statistics will be used to summarize baseline and study outcomes. For continuous variables, number of available observations, mean, standard deviation, median, minimum and maximum values will be provided. For categorical variables, frequency and percentage will be used. Unless otherwise specified, statistical assessments will be based on 2-sided tests at an alpha level of 0.05, which include Student-t or Wilcoxon rank-sum or ANOVA test for continuous variables, and Chi-square or Fisher's exact test for categorical variables. Multivariate regression models will be used to assess impacts of potential confounding variable. Statistical analysis will be performed using [REDACTED] (SAS Institute Inc., Cary, NC) or other valid statistical software.

The primary effectiveness analysis will be based on all evaluable data from this study. A per protocol analysis will be performed based on all subjects who are compliant with the study protocol, i.e. who provide valid informed consents and do not experience any major protocol deviations.

For safety assessments, adverse events (AEs) will be summarized using frequency counts and percentages. Descriptive statistics will be provided by monitoring group and by severity and relationship. Additionally, differences between the two monitoring groups will be summarized along with 95% confidence intervals. Individual listings of adverse events, including event type, start date, duration, severity, and device-relatedness will be provided as appropriate. The safety analysis will be based on all patients participated in the study.

Further, a health economic analysis will be performed based on healthcare economic and resource utilization data collected in this study. Monitoring effectiveness, QoL in the form of Quality-Adjusted Life-Years (QALYs), life-years gained and other data collected in this study may be used as inputs to the model.

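### The visible methods give length of stay an equality test (ANOVA, t or Wilcoxon) although the objective is non-inferiority on a mean ratio, and 132 per group has the stated power only at one-sided 0.05

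*Protocol*

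**What the plan says.** Three sets of statements bear on the LOS analysis.

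- **Test.** The Statistics row of the protocol synopsis reads "One-way analysis of variance will be used to compare continuous variables (e.g., age, length of study" and sets P below 0.05 as the default for significance. The phrase denotes LOS, because protocol 13.2 (repeated in SAP 7.9) says "The primary study endpoint is hospital of length of study (LOS), which is calculated from date of admission and discharge". For continuous variables, protocol 13.3 and SAP 7.2 give a list, "Student-t or Wilcoxon rank-sum or ANOVA test for continuous variables", two-sided at 0.05 unless something else is specified.
- **Objective.** Protocol 13.2 and SAP 7.9 say "The primary objective is to demonstrate that LOS of the SM group is similar (non-inferior) to the TM group". Superiority is assessed afterwards if non-inferiority is met.
- **Sample size.** Protocol 13.1 and SAP 6 start from "With a pre-specified non-inferiority margin of 0.2 for the mean ratio", a "common coefficients of variation of 0.65" and equal LOS in the two groups ("we assume a similar LOS distribution for both monitoring groups"). They give 132 per group for more than 80% power at a significance level of 0.05, without saying whether that is one-sided or two-sided.

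The formal hypotheses in protocol 13.2 and the superiority hypothesis in SAP 7.9 are blacked out. The visible text gives no confidence limit to compare with the margin and no analysis scale for LOS.

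**The concern.** A one-way ANOVA F test takes equality of means as its null hypothesis; it has no direction and no margin. The t test, used in its ordinary form, has the same null. The Wilcoxon test compares ranks and does not estimate a mean ratio. A non-significant result from any of them does not show that the SM/TM ratio is below 1.20, and a significant one does not show that it is above 1.20.

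The primary claim of the study depends on that comparison. An analyst working from the visible sections would not know which statistic decides non-inferiority, on which scale, or at which one-sided level. Power at 132 per group moves from about 80% to about 70% with the level alone.

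**Working it through.** **Inputs.** Margin 0.2 on the mean ratio, CV 0.65 in both groups, true ratio 1, 132 per group, alpha 0.05 (protocol 13.1, SAP 6); default two-sided 0.05 (protocol 13.3, SAP 7.2). Assumptions: the margin means an upper bound of 1.20, since a longer stay is worse (the visible text does not print 1.20), and LOS is log-normal where the log scale is used.

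**Step 1: reproduce 132 on the log scale.**
- SD = sqrt(ln(1 + 0.65²)) = 0.594; margin = ln(1.20) = 0.1823.
- n = 2 × 0.594² × (1.645 + 0.842)² / 0.1823² = 131.1, so 132 per group at one-sided 0.05.
- Power at 132 by the noncentral t: **80.1%**.

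**Step 2: reproduce it on the raw scale.** Take a difference in means with the margin fixed at 0.2 × mean and SD 0.65 × mean.
- n = 2 × 0.65² × (1.645 + 0.842)² / 0.2² = 130.6, so 131 per group (132 by the noncentral t).
- Power at 132: **80.2%**.

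The stated figure therefore does not identify the scale. It does depend on one-sided 0.05.

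**Step 3: repeat at two-sided 0.05 (one-sided 0.025).**

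| Analysis | Power at 132 | n per group for 80% (noncentral t) |
|---|---|---|
| Log scale, margin ln(1.20) | 70.1% | 168 |
| Raw difference, fixed 20% margin | 70.2% | 167 |

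The recruitment allowance does not close the gap. With 220 recruited and the protocol's 30% attrition, 220 × 0.7 = 154 remain, and log-scale power is 76.6%. With the SAP's 140 per group and no losses it is 72.6%.

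**Step 4: a raw-scale ratio test, if one were chosen.** A Fieller-type test uses the contrast mean(SM) − 1.2 × mean(TM).
- SE = 0.65 × sqrt((1 + 1.44)/132) = 0.0884 in units of the mean; 0.2/0.0884 = 2.26.
- Power = Φ(2.26 − 1.645) = 73% at one-sided 0.05, and Φ(2.26 − 1.96) = 62% at one-sided 0.025.
- For 80% power it needs 160 or 203 per group.

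Neither document names this test. It shows only how much the unstated choice matters.

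**Step 5: what non-significance would mean.** Let the true ratio be 1.20, exactly at the margin, with 132 per group and a two-sided 0.05 test of equality.
- Log scale: power 70.1%, so non-significant in 100 − 70.1 = about 30% of trials.
- Raw-scale ANOVA with log-normal LOS and CV 0.65 in both groups: non-significant in about 37% of trials (simulation). The SD in the SM group is then 1.2 times that in the TM group, so the SE is again 0.0884, and 1 − Φ(2.26 − 1.96) = 38% agrees.

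A valid non-inferiority test would pass at that point in 5% of trials (one-sided 0.05) or 2.5% (one-sided 0.025).

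**The case against.** The strongest reply is that the quoted sentences are defaults. The synopsis is a summary, and it, protocol 13.3 and SAP 7.2 all allow for other specifications. Non-inferiority with a margin is specified separately. A redacted block follows the primary objective in protocol 13.2 and may state the hypotheses, the direction of the margin, the sidedness or the decision rule. A two-group t or ANOVA model can also supply a confidence interval to set against a margin, so those methods are not incapable of the task.

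Most of this stands as a limit on the point. Redacted text cannot be counted as missing, and a reader might infer that a non-significant ANOVA will be taken as proof of non-inferiority; the documents nowhere say so. But the synopsis visibly gives LOS as an example of what ANOVA will compare, and the general-methods sentences do not exempt it. No visible sentence says that a confidence limit will be drawn from the model and compared with 1.20.

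A reader might also infer that 132 presupposes a log-scale analysis and that any raw-scale analysis is underpowered. The arithmetic does not support that: a raw difference with a fixed margin of 20% of the mean gives the same number. The lower power of 73% belongs to a Fieller-type test that the plan does not name.

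Finally, the synopsis wording is a slip for length of stay. The reading is still secure, because protocol 13.2 and SAP 7.9 attach the abbreviation LOS to the same words.

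**Conclusion.** The point holds for the visible text. The tests named for LOS assess equality, whereas the objective and the sample size concern a margin of 0.2 on the mean ratio. The visible sections leave open the scale, the sidedness and the confidence limit for the primary comparison.

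The 132 per group is reproducible and is not an error. It requires one-sided 0.05; at the default two-sided 0.05, power is about 70% and not more than 80%, on either scale. These figures rest on CV 0.65, a true ratio of 1, the margin read as 1.20 and, for the log scale, log-normal LOS. The redacted hypotheses may settle part of this. The visible sentences would still need to agree with them, so the change should be made, but the documents do not support saying that the plan has no non-inferiority test.

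**What to change.** - **Synopsis:** remove LOS from the ANOVA example.
- **Protocol 13.3 and SAP 7.2:** limit the t/Wilcoxon/ANOVA sentences to baseline and secondary variables.
- **Protocol 13.3, SAP 7.2 and SAP 7.9:** state that non-inferiority is concluded if the upper confidence limit of the SM/TM LOS ratio is below 1.20, and name the model. One option is a linear model on log(LOS in minutes) with monitoring group as a term. This targets a ratio of geometric means, which equals the mean ratio only if the log-scale variance is the same in both groups; the text should say so.
- **Confidence level:** either specify one-sided 0.05 (the upper limit of a 90% interval), which matches the 132, or keep two-sided 0.05 and restate the power at 132 per group as about 70%.
- **Redacted hypotheses:** check that the new wording agrees with them.

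The cost is a text amendment to both documents, with no new data collected. The first choice of level leaves the sample size as it is. The second means accepting the lower stated power, or about 167 to 168 evaluable subjects per group to restore 80%. The choices of scale and level should be fixed before LOS is compared between the groups.
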